7.4 Derived Data

VR-12 domains/subscales

Table 3 displays the values from the scores from the original VR-12 instrument, an analogue of the SF-12 Quality of Life (QoL) (2) instrument, based on potential responses to

CONFIDENTIAL AND PROPRIETARY

This document contains information that is confidential and proprietary to Smith & Nephew PLC and Smith & Nephew, Inc. and is intended for use only by Smith & Nephew and its manufacturer. It shall not be reproduced or copied in whole or in part, nor shall the contents be disclosed by any means without prior written permission from Smith & Nephew, nor shall anyone make any use of it that is contrary to the expressed or implied wishes of Smith & Nephew.

Statistical Analysis Plan	 smith&nephew
A Retrospective Study of the NAVIO Robotic-assisted Surgical System	Number: 16-NPFS-11
	Version: Final 1.0, Jan 29, 2018
	Page: 15 of 25

the questions. These values are transformed into scores for use in the different conceptual sub-domains (Table 3) that make up the PCS MCS domains.

The transformation of raw scale scores provided in Table 3 to transformed scores in Table 4 (0-100 transformed range) utilizes the following algorithm:

Transformed scale score =

$\{(Actual\ raw\ score - Lowest\ possible\ raw\ score) / Possible\ raw\ score\ range\} \times 100$.

CONFIDENTIAL AND PROPRIETARY

This document contains information that is confidential and proprietary to Smith & Nephew PLC and Smith & Nephew, Inc. and is intended for use only by Smith & Nephew and its manufacturer. It shall not be reproduced or copied in whole or in part, nor shall the contents be disclosed by any means without prior written permission from Smith & Nephew, nor shall anyone make any use of it that is contrary to the expressed or implied wishes of Smith & Nephew.

Statistical Analysis Plan	 smith&nephew
A Retrospective Study of the NAVIO Robotic-assisted Surgical System	Number: 16-NPFS-11
	Version: Final 1.0, Jan 29, 2018
	Page: 16 of 25

Table 3: VR-12 scoring for individual questions

Item (Question) number	Response Choices	Likely scores on original response	Final Item Value *
Q1	Excellent Very Good Good Fair Poor	1 2 3 4 5	5.0 4.4 3.4 2.0 1.0
Q2a, Q2b	Yes, limited a lot Yes, limited a little No, not limited at all	1 2 3	1 2 3
Q3a, Q3b, Q4a, Q4b, Q6c, Q7	All of the time Most of the time Some of the time A little of the time None of the time	1 2 3 4 5	1 2 3 4 5
Q5	Not at all A little bit Moderately Quite a bit Extremely	1 2 3 4 5	5 4 3 2 1
Q6a, Q6b	All of the time Most of the time Some of the time A little of the time None of the time	1 2 3 4 5	5 4 3 2 1

* Note, the higher the score on the final item value, the more favorable the response.

CONFIDENTIAL AND PROPRIETARY

This document contains information that is confidential and proprietary to Smith & Nephew PLC and Smith & Nephew, Inc. and is intended for use only by Smith & Nephew and its manufacturer. It shall not be reproduced or copied in whole or in part, nor shall the contents be disclosed by any means without prior written permission from Smith & Nephew, nor shall anyone make any use of it that is contrary to the expressed or implied wishes of Smith & Nephew.

Statistical Analysis Plan	 smith&nephew
A Retrospective Study of the NAVIO Robotic-assisted Surgical System	Number: 16-NPFS-11
	Version: Final 1.0, Jan 29, 2018
	Page: 17 of 25

Table 4: VR-12 Sub-domains of the PCS¹ and MCS².

Scale/Domain	Sum of Final Items from Table 3	Lowest and Highest Possible raw scores	Possible raw score range
Physical Functioning ¹	Q2a, Q2b	(2, 6)	4
Role Physical ¹	Q3a, Q3b	(2, 10)	8
Bodily Pain ¹	Q5	(1, 5)	4
General health ¹	Q1	(1, 5)	4
Vitality ²	Q6b	(1, 5)	4
Social Functioning ²	Q7	(1, 5)	4
Role Emotional ²	Q4a, Q4b	(2, 10)	8
Mental Health ²	Q6a, Q6c	(2, 10)	8

[1] Physical Component Score.

[2] Mental Component Score.

7.5 Baseline Data

CONFIDENTIAL AND PROPRIETARY

This document contains information that is confidential and proprietary to Smith & Nephew PLC and Smith & Nephew, Inc. and is intended for use only by Smith & Nephew and its manufacturer. It shall not be reproduced or copied in whole or in part, nor shall the contents be disclosed by any means without prior written permission from Smith & Nephew, nor shall anyone make any use of it that is contrary to the expressed or implied wishes of Smith & Nephew.

Statistical Analysis Plan	 smith&nephew Number: 16-NPFS-11 Version: Final 1.0, Jan 29, 2018 Page: 18 of 25
A Retrospective Study of the NAVIO Robotic-assisted Surgical System	

The following demographic and baseline variables whose information is available either at the pre-operative or the operative visit would be summarized using descriptive characteristics for continuous¹ or categorical² data as follows:

- Age¹ (in years),
- Sex² (males or females),
- Race²,
- Weight¹ (in kg),
- Height¹ (in cm),
- Body Mass Index¹,
- Primary diagnosis²,
- Smoking status at time of surgery²
- Duration of surgery (in hours)¹,
- Type of surgical approach²,
- Type of knee system implanted (Smith & Nephew Inc. Unicondylar Knee System or Other Smith & Nephew Inc. Unicondylar System)²,
- Type of UKR used (medial or lateral)²,
- Intra-operative complications² and,
- Blood loss prevention method².

CONFIDENTIAL AND PROPRIETARY

This document contains information that is confidential and proprietary to Smith & Nephew PLC and Smith & Nephew, Inc. and is intended for use only by Smith & Nephew and its manufacturer. It shall not be reproduced or copied in whole or in part, nor shall the contents be disclosed by any means without prior written permission from Smith & Nephew, nor shall anyone make any use of it that is contrary to the expressed or implied wishes of Smith & Nephew.

Statistical Analysis Plan	 smith&nephew
A Retrospective Study of the NAVIO Robotic-assisted Surgical System	Number: 16-NPFS-11
	Version: Final 1.0, Jan 29, 2018
	Page: 19 of 25

Age would further be summarized categorically by stratifying into: < 60 years versus \geq 60 years. BMI would also be further summarized categorically by stratifying into: < 30 kg/m² versus \geq 30 kg/m².

7.6 Disposition of Patients

- Subject disposition would be summarized as frequency (n) and percentage (%) of subjects who complete and who do not complete the study. For those who do not complete the study, the primary reason for discontinuation would additionally be summarized.
- Subject accountability information would also be presented. This would be summarized by visit for the number of subjects that are theoretically due, subject deaths, subjects who had a revision and, subjects who terminated from the study for any reason. Additional information that would be summarized on the subject accountability table would include but not limited to the number of subjects presenting at each visit, number of subjects expected at each visit.

7.7 Protocol Deviations

A listing of deviations encountered during the study would be listed. Deviations that would lead to the exclusion of subjects in the per protocol population would be appropriately identified and flagged.

7.8 Measurement of Treatment Compliance

N/A.

7.9 Multiplicity

N/A.

7.10 Analysis of Primary Endpoint

CONFIDENTIAL AND PROPRIETARY

This document contains information that is confidential and proprietary to Smith & Nephew PLC and Smith & Nephew, Inc. and is intended for use only by Smith & Nephew and its manufacturer. It shall not be reproduced or copied in whole or in part, nor shall the contents be disclosed by any means without prior written permission from Smith & Nephew, nor shall anyone make any use of it that is contrary to the expressed or implied wishes of Smith & Nephew.

Statistical Analysis Plan	smith&nephew
A Retrospective Study of the NAVIO Robotic-assisted Surgical System	Number: 16-NPFS-11
	Version: Final 1.0, Jan 29, 2018
	Page: 20 of 25

For the primary endpoint, cumulative proportion (or percentage) of subjects with implant survivorship at 2+ years (96 weeks), the following is the hypothesis would be performed:

H_0 (null): $S(t) = \pi \leq (\pi_0 - \delta)$ versus

H_a (alternate): $S(t) = \pi > (\pi_0 - \delta)$,

where π = expected percentage of subjects with implant survivorship at 2 years, π_0 = historical control implant survivorship (95.7%) and δ = margin of non-inferiority (7%).

Because not all subjects would be fully evaluated through study completion, the Kaplan-Meier product limit survival estimate would be used to estimate implant survivorship, $S(t)$ where $S(t)$ is the proportion of subjects at time t , without a device revision. Time to implant revision would be the endpoint of interest in the determination of implant survivorship.

Cumulative proportions of subjects with implant survivorship at 2 years would be calculated and displayed accordingly. Subjects who complete the study without a revision would be censored at their last known date in the study. A subject who prematurely discontinues from study as a result of death or for any other reason would be censored at the date this event occurred. A subject who is lost to follow-up would be censored at the last known contact date. The Kaplan-Meier estimate for implant survivorship would be presented with the corresponding two-sided 95% Confidence Intervals (CIs). This study's hypothesis test would only be carried out at the end of the study at 2+ years (96 weeks). From this test, if the lower limit (LL) of the 95% two-sided CI for $S(t = 2 \text{ years}) > (\pi_0 - \delta) = 88.7\%$, then H_0 will be rejected in favor of H_a (i.e. demonstration of non-inferiority of the investigational device) otherwise H_0 would not be rejected. Kaplan-Meier estimates for implant survivorship would also be non-inferentially estimated at the intermediate time points of 6 months (24 weeks), 1 year (48 weeks), and at 18 months (72 weeks) as well as subsequently at 30 months (120 weeks).

The primary endpoint would be analyzed using the safety population as the primary analysis population while the per protocol population would be used for sensitivity analysis.

7.11 Analysis of Secondary Endpoints

CONFIDENTIAL AND PROPRIETARY

[figure not shown]
This document contains information that is confidential and proprietary to Smith & Nephew PLC and Smith & Nephew, Inc. and is intended for use only by Smith & Nephew and its manufacturer. It shall not be reproduced or copied in whole or in part, nor shall the contents be disclosed by any means without prior written permission from Smith & Nephew, nor shall anyone make any use of it that is contrary to the expressed or implied wishes of Smith & Nephew.

Statistical Analysis Plan	 smith&nephew
A Retrospective Study of the NAVIO Robotic-assisted Surgical System	Number: 16-NPFS-11
	Version: Final 1.0, Jan 29, 2018
	Page: 21 of 25

- The KSS endpoints would be evaluated by deriving the scores for objective knee indicators, patient satisfaction, patient expectation and functional activities. Each of these derived scores would be summarized using descriptive summary characteristics for continuous variables at the 2+ year (24 months) follow-up visit.
- The post-operative 24 month visit of the PCS domain, MCS domain as well as sub-domains of the PCS and MCS would be summarized using descriptive summary characteristics for continuous variables.
- The following are the descriptive summary of the anterior/posterior and lateral radiographic assessments by visit of the assessment:
 - Presence of heterotrophic ossification, patellar subluxation, patellar dislocation would be summarized as count (n) and percent (%).
 - For component orientation, femur/tibia angle, tibia component, posterior slope of tibia tray would be summarized using descriptive characteristics for continuous variables.
 - For radiolucencies, overall summary as n and % of subjects who have radiolucent lines would be summarized. Furthermore, the distribution of the number of radiolucent lines and corresponding dimensions (in mm) by visit within the femoral zone, Tibial AP zone, and Tibial ML zone would also be categorically summarized.
 - For migration, categorical summary characteristics as n and % by visit would be used to summarize the presence of tibial migration/subsidence and femoral migration/subsidence.

CONFIDENTIAL AND PROPRIETARY

This document contains information that is confidential and proprietary to Smith & Nephew PLC and Smith & Nephew, Inc. and is intended for use only by Smith & Nephew and its manufacturer. It shall not be reproduced or copied in whole or in part, nor shall the contents be disclosed by any means without prior written permission from Smith & Nephew, nor shall anyone make any use of it that is contrary to the expressed or implied wishes of Smith & Nephew.

Statistical Analysis Plan	 smith&nephew
A Retrospective Study of the NAVIO Robotic-assisted Surgical System	Number: 16-NPFS-11
	Version: Final 1.0, Jan 29, 2018
	Page: 22 of 25

- For osteolysis, categorical summary characteristics by visit using n and %.

All secondary endpoints would be summarized using the safety population. All data for the secondary endpoints would be analyzed as observed cases, i.e. there would be no imputation for missing values.

7.12 Analysis of Exploratory Endpoints

N/A.

7.13 Analysis of Safety Endpoints

CONFIDENTIAL AND PROPRIETARY

This document contains information that is confidential and proprietary to Smith & Nephew PLC and Smith & Nephew, Inc. and is intended for use only by Smith & Nephew and its manufacturer. It shall not be reproduced or copied in whole or in part, nor shall the contents be disclosed by any means without prior written permission from Smith & Nephew, nor shall anyone make any use of it that is contrary to the expressed or implied wishes of Smith & Nephew.

Statistical Analysis Plan	 smith&nephew
A Retrospective Study of the NAVIO Robotic-assisted Surgical System	Number: 16-NPFS-11
	Version: Final 1.0, Jan 29, 2018
	Page: 23 of 25

- An overall summary AE table that would summarize as number (n) and percentages (%), the overall incidence according to subjects with at least one AE; subjects with at least one AE by worst severity (mild, moderate, or severe); subjects with at least one AE by worst outcome; subjects with an AE that led to study discontinuation; subjects with at least one AE by worst relatedness to investigational device; subjects with AEs by worst relationship to the NAVIO device; SAEs; ADEs; SADEs; UADEs and; AEs of special interest would be summarized. A Smith and Nephew Adverse Event Monitoring Board (AEMB) may be convened to review the list of and subsequently classify AEs into special interest AEs for additional AE summaries.
- Tables that summarize the incidence of AEs (each based on criteria previously specified in the overall summary table) would be generated. Each table would include the numbers (n) and percentages (%) of subjects with each AE as well as the cumulative events/episodes per AE.

All summaries and listings for the safety endpoints would use the safety population as the analysis population.

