## **8. SAFETY REPORTING**

Adverse Events (AE) related to the study device (Navio), the unicondylar implant, or procedure including Adverse Device Effects (ADE), Serious Adverse Device Effects (SADE), Unanticipated Serious Adverse Device Effect (USADE), and Device Deficiencies (DevD) occurring from the time of the study procedure until revision or study completion must be recorded on the appropriate CRF and reported. If the event is known to have been previously reported to Smith & Nephew, this must be noted on the CRF. After consent, in addition to all events related to Navio, the unicondylar implant or the procedure, all serious adverse events (SAE), regardless of causality, must be recorded on the appropriate CRF and reported to sponsor and IRB if necessary. Events leading to a revision should be reported at all times regardless of causality.

Adverse Device Effects (ADE) occurring after study completion will be handled as product complaints reportable by the Sponsor and will not be entered into the study database.

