This document contains information that is confidential and proprietary to Smith & Nephew PLC and Smith & Nephew, Inc. and is intended for use only by Smith & Nephew and its manufacturer. It shall not be reproduced or copied in whole or in part, nor shall the contents be disclosed by any means without prior written permission from Smith & Nephew, nor shall anyone make any use of it that is contrary to the expressed or implied wishes of Smith & Nephew.

Statistical Analysis Plan	 smith&nephew
A Retrospective Study of the NAVIO Robotic-assisted Surgical System	Number: 16-NPFS-11
	Version: Final 1.0, Jan 29, 2018
	Page: 7 of 25

Subjects enrolled would be followed-up for evaluation of safety and effectiveness of the device. Subjects would retrospectively be evaluated pre-operatively and operatively and prospectively at subsequent available post-operative follow-up visits for up to 2 years (24 months) or beyond. In order to evaluate the effectiveness of the NAVIO system-assisted investigational device, information on the revision rate (or survivorship) from a currently used device from an appropriate registry would be used as historical control. The historical control's revision (or survivorship) rate which was obtained from an orthopedic registry is specified in future sections of the SAP.

The study schematic displayed in Table 1 provides a succinct overview of the parameters evaluated within the study design.

CONFIDENTIAL AND PROPRIETARY

This document contains information that is confidential and proprietary to Smith & Nephew PLC and Smith & Nephew, Inc. and is intended for use only by Smith & Nephew and its manufacturer. It shall not be reproduced or copied in whole or in part, nor shall the contents be disclosed by any means without prior written permission from Smith & Nephew, nor shall anyone make any use of it that is contrary to the expressed or implied wishes of Smith & Nephew.

Statistical Analysis Plan	 smith&nephew
A Retrospective Study of the NAVIO Robotic-assisted Surgical System	Number: 16-NPFS-11 Version: Final 1.0, Jan 29, 2018 Page: 8 of 25

Table 1: Study schematic.

	Retrospective Data Collection ¹				Prospective Data Collection ²
	Screening and Enrollment	Pre-operative	Operative / Discharge	Follow-up	
Informed Consent	✓ ³				
Inclusion/Exclusion	✓				
Demographics/ Medical History		✓			
Operative and Discharge Data Collection			✓		
Implant Status ⁴				✓	✓
Knee Society Score (KSS)		✓		✓	✓
VR-12		✓		✓	✓
Radiographic Assessment		✓	✓	✓	✓

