4.1 Primary Objective

CONFIDENTIAL AND PROPRIETARY

This document contains information that is confidential and proprietary to Smith & Nephew PLC and Smith & Nephew, Inc. and is intended for use only by Smith & Nephew and its manufacturer. It shall not be reproduced or copied in whole or in part, nor shall the contents be disclosed by any means without prior written permission from Smith & Nephew, nor shall anyone make any use of it that is contrary to the expressed or implied wishes of Smith & Nephew.

Statistical Analysis Plan	smith&nephew
A Retrospective Study of the NAVIO Robotic-assisted Surgical System	Number: 16-NPFS-11
	Version: Final 1.0, Jan 29, 2018
	Page: 9 of 25

The primary objective of this study is to evaluate the 2-year safety and effectiveness of the NAVIO System's assisted implanted UKR in subjects aged ≥ 18 years.

5. Study Endpoints

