5.4 Safety Endpoints

Safety endpoints are as follows:

- Incidence of AEs,
- Incidence of AEs by severity,
- Incidence of AEs by relationship to knee implant (study device),
- Incidence of AEs by relationship to NAVIO System,
- Incidence of AEs that led to discontinuation,
- Incidence of AEs by outcome,
- Incidence of serious adverse events (SAEs),
- Incidence of adverse device effects (ADE),
- Incidence of serious adverse device effects (SADEs),
- Incidence of unanticipated adverse device effects (UADEs),
- AEs of special interest,
- Listing of revisions and details of components removed during revision.

6. Statistical Considerations

CONFIDENTIAL AND PROPRIETARY

This document contains information that is confidential and proprietary to Smith & Nephew PLC and Smith & Nephew, Inc. and is intended for use only by Smith & Nephew and its manufacturer. It shall not be reproduced or copied in whole or in part, nor shall the contents be disclosed by any means without prior written permission from Smith & Nephew, nor shall anyone make any use of it that is contrary to the expressed or implied wishes of Smith & Nephew.

Statistical Analysis Plan	 smith&nephew
A Retrospective Study of the NAVIO Robotic-assisted Surgical System	Number: 16-NPFS-11
	Version: Final 1.0, Jan 29, 2018
	Page: 12 of 25

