7.2 Analysis Populations

Safety Population

This is defined as the population of subjects who receive the investigational study device.

Per Protocol Population

The per protocol population is the subset of subjects in the safety population who are compliant with the protocol by satisfying the following criteria: (a) meeting all inclusion/exclusion criteria (b) attend follow-up assessments and do not have significant protocol deviations.

Subjects who have a device revision would retain membership in the per protocol population unless any of the above two specifications is met. The final decision on which deviations would be classified as significant would be finalized prior to database lock.

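### Apart from revision, no adverse-event figure in SAP 7.13 estimates a 2-year risk: crude percentages are taken over unequal follow-up with no upper limit

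*SAP*

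**What the plan says.** SAP 4.1 sets the aim to "evaluate the 2-year safety and effectiveness of the NAVIO System's assisted implanted UKR in subjects aged" 18 and over. Protocol 2 has the same 2-year objective and names AE incidence and frequency among the ways it will be shown.

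The analysis of AEs has no matching time point. SAP 5.4 lists endpoints such as "Incidence of AEs by relationship to NAVIO System" without a window. SAP 7.13 specifies the statistic: "Each table would include the numbers (n) and percentages (%) of subjects with each AE as well as the cumulative events/episodes per AE". On the denominator it says: "All summaries and listings for the safety endpoints would use the safety population as the analysis population". SAP 7.2 describes that population thus: "This is defined as the population of subjects who receive the investigational study device". No minimum follow-up applies.

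On the collection period, Protocol 8 requires that related events "occurring from the time of the study procedure until revision or study completion must be recorded on the appropriate CRF and reported". SAP 3 describes evaluation "prospectively at subsequent available post-operative follow-up visits for up to 2 years (24 months) or beyond".

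Revision is treated differently. SAP 7.10 estimates implant survivorship by Kaplan-Meier, with a 95% CI at 2 years, and gives incomplete follow-up as the reason.

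**The concern.** A crude percentage equals a 2-year risk only if every subject is observed for 2 years and nothing later is counted. Neither condition is built in. In the SAP 7.13 tables, a subject lost at 6 months stays in the denominator as if observed throughout, and a related event at month 34 counts in full. Short follow-up pulls the percentage down and long follow-up pushes it up, so the result depends partly on how long each site happened to follow its patients.

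The AE, ADE and SADE tables are the natural place to look for 2-year safety beyond revision. As planned, they give a reader neither a 2-year risk nor the time at risk needed to judge how far the crude figure is from one.

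**Working it through.** **What the documents fix.** They state no AE rate, AE precision target or follow-up distribution, so there is no AE figure to reproduce. The sample size (115, or 128 with attrition) concerns revision only.

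**Why follow-up is unequal by design.**

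- *Short.* Protocol 5.2 allows data on deceased and lost subjects under a consent waiver, and lets subjects without a 2-year visit consent to the retrospective phase only. Protocol 7.1 F stops collection at revision. Protocol 5.3 sets no minimum time since surgery.
- *Long.* Protocol 3 puts the final visit at 2 years minus 3 months, or later. Protocol 5.1 starts screening from each investigator's first case. SAP Table 2 has windows to 36 months, but only for KSS and VR-12.
- *No correction.* SAP 7.13 has no cut-off, person-time or time-to-event method. The censoring rule in SAP 7.3 cannot act on a plain n (%) table.

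**Illustration.** The true 2-year risk and all follow-up mixes are assumptions. Take a true 2-year risk of 10%.

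Constant hazard: h = -ln(0.90)/2 = 0.0527 per year, and F(t) = 1 - exp(-h t). Hence F(0.5) = 0.0260, F(1) = 0.0513, F(2) = 0.1000, F(3) = 0.1462 and F(4) = 0.1900. The expected crude percentage is the sum of w × F(t), where w is the share of subjects followed for time t.

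- 10% followed 0.5 y, 90% followed 2 y: 0.1 × 0.0260 + 0.9 × 0.1000 = 0.0926. The 10% share matches the attrition allowance in Protocol 9.1; the 0.5 y is assumed.
- 60% followed 2 y, 40% followed 3 y: 0.6 × 0.1000 + 0.4 × 0.1462 = 0.1185. The 3 y matches the last window in SAP Table 2, which is not a cap.
- Extreme low, 40% at 0.5 y and 60% at 2 y: 0.4 × 0.0260 + 0.6 × 0.1000 = 0.0704.
- Extreme high, 10% at 1 y and 90% at 4 y: 0.1 × 0.0513 + 0.9 × 0.1900 = 0.1761.

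Front-loaded events: suppose 80% of the 2-year risk falls in the first 90 days (0.25 y), with a constant hazard afterwards. Then F(t) = 1 - 0.92 × exp(-g (t - 0.25)), with g = -ln(0.90/0.92)/1.75 = 0.0126.

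| Assumed follow-up mix | Constant hazard | Front-loaded |
|---|---|---|
| 10% 0.5 y, 90% 2 y | 9.3% | 9.8% |
| 60% 2 y, 40% 3 y | 11.8% | 10.4% |
| 40% 0.5 y, 60% 2 y | 7.0% | 9.3% |
| 10% 1 y, 90% 4 y | 17.6% | 11.9% |

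For true risks of 5% and 20%, the two extreme mixes under a constant hazard give 3.5% to 9.0% and 14.2% to 33.5%. A cumulative-incidence estimate at 2 years targets the true figure in every mix, provided censoring is non-informative.

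**The case against.** Crude incidence is the customary AE display, and it is what the protocol asks for: Protocol 9.4 plans numbers, types and rates with binomial or asymptotic intervals. The SAP never labels an AE percentage as a 2-year risk. No hypothesis, benchmark or decision rests on these tables, since the historical control is for revision alone. SAP 7.6 already shows, by visit, who was due, seen, dead, revised or terminated. Collection centres on device-, implant- and procedure-related events, which may cluster soon after surgery, where the distortion is small.

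Most of this stands, and it limits the point. It does not remove it: the objective is dated, the AE tables are not, and the SAP uses a time-to-event method for revision in the same subjects because follow-up is incomplete. If the distortion is small, readers of the tables cannot tell, because person-time and numbers at risk for AEs are not reported.

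A reader might go further and infer that no safety result is a 2-year risk, or that half the objective goes unanswered. The documents do not support that. Revision is documented on the AE form (Protocol 8.1 G), is listed among the safety endpoints (SAP 5.4), and has a 2-year Kaplan-Meier estimate with CI (SAP 7.10). Nor do they support a claim of large bias, which needs extreme follow-up mixes and a constant hazard that nothing in the text establishes.

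**Conclusion.** The point holds for the AE, ADE and SADE tables in SAP 7.13, with revision excepted. Those tables mix follow-up lengths and estimate no 2-year risk, although 2-year safety is a stated objective. The direction and size of the error are unknown from the documents. Under the assumptions above, a true 10% would show as roughly 9% to 12% with moderate mixes or with front-loaded events, and about 7% to 18% with extreme mixes and a constant hazard. The primary non-inferiority test is unaffected. The change should be made because it is specific and cheap, not because any decision is at risk.

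A separate discrepancy needs its own correction: SAP 7.13 omits the 95% CIs for AE rates that Protocol 9.4 calls for, and SAP 7.15 does not list this as a change.

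**What to change.** Keep the crude tables in SAP 7.13 and add the following.

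1. For AEs related to the device, implant or procedure, and for ADEs and SADEs, report the cumulative incidence of the first event at the same 2-year time point as the primary endpoint, with 95% CI.
2. Settle that time point first. SAP 5.1 and 7.10 equate 2+ years with 96 weeks (96 × 7 = 672 days), SAP Table 2 ends month 24 at day 730, and Protocol 3 accepts a final visit 3 months early. A subject seen at month 21 completes the study but would be censored before either date.
3. Censor at the last date of AE ascertainment. Treat death and revision as competing events where they end collection (Aalen-Johansen).
4. Tabulate events after the time point separately. Show median follow-up, person-years and number at risk.
5. Do not apply this to all-cause SAEs across both phases. Protocol 8 requires these only after consent, so ascertainment differs by phase and censoring would not cure that.

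The cost is SAP wording, a few extra tables and a rule for partial onset dates in retrospective records. The Kaplan-Meier analysis of revision already needs event and last-contact dates for the same subjects.
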